3.2 Secondary Objective(s) & Hypothesis(es)

- (1) **Objective:** To compare ORR and DCR per RECIST 1.1 as assessed by BICR in subjects treated with a combination of pembrolizumab plus axitinib versus sunitinib monotherapy. DOR will also be evaluated.

Hypothesis: The combination therapy of pembrolizumab plus axitinib is superior to sunitinib monotherapy with respect to ORR as assessed by BICR per RECIST 1.1.

- (2) **Objective:** To evaluate PFS rate per RECIST 1.1 as assessed by BICR at 12, 18, and 24 months based on data adequacy; to evaluate OS rates at 12, 18, and 24 months based on data adequacy.
- (3) **Objective:** To evaluate and compare safety and tolerability profiles in subjects treated with pembrolizumab plus axitinib versus sunitinib monotherapy.
- (4) **Objective:** To compare time to deterioration (TTD) based on the Functional Assessment of Cancer Therapy Kidney Symptom Index—Disease-Related Symptoms (FKSI-DRS) scale in subjects treated with pembrolizumab plus axitinib versus sunitinib monotherapy.
- (5) **Objective:** To assess the longitudinal score changes from baseline to 42 weeks as measured by European Organization for the Research and Treatment of Cancer (EORTC) QLQ-C30 global health status/quality of life scale.

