4.2.3.3 Health-related Quality of Life Endpoints

FKSI-DRS, EORTC-QLQ-C30, and EuroQol EQ-5D-3L are not pure efficacy or safety endpoints because they are affected by both disease progression and treatment tolerability.

The FKSI-DRS scale and global health status/quality of life scale from EORTC-QLQC30 are the key PRO endpoints. Although no formal hypothesis was formulated, the p-value on treatment comparisons will be provided. No multiplicity adjustment was performed.

The 9 items of the FKSI-DRS are summarized into a symptom scale ranging in score from zero (0) to thirty-six (36), with zero being the worst possible score and 36 being the best possible score [52]. The minimum important change in the FKSI-DRS used to define symptom progression is approximately a change of 2 points and that definition has been used for this mRCC symptom scale in other mRCC trials [19, 52, 53]. The Time-to-Deterioration of FKSI-DRS is defined as:

[figure not shown]
- The time to first onset of 2 or more decreases from baseline.
- The time to first onset of 2 or more decrease from baseline and confirmed by the second adjacent 2 or more decrease from baseline.
- The time to first onset of 2 or more decrease from previous nadir and confirmed by the second adjacent 2 or more decrease from nadir.

[figure not shown]
The longitudinal score changes of the EORTC QLQ-C30 global health status/quality of life scale (i.e., items 29 and 30) from baseline and the proportions of deterioration/stable/improvement at 42 weeks (i.e., based on expected median PFS of 11 months in the control group) into the study will be described. A 10-point decrease is often considered as the minimal clinical meaningful difference. Other supportive analyses include 5 functional dimensions (physical, role, emotional, cognitive, and social), 3 symptom items (fatigue, nausea/vomiting, and pain), 6 single items (dyspnea, sleep disturbance, appetite loss, constipation, diarrhea, and financial impact), and a global health and quality of life scale.

EuroQol EQ-5D-3L is another set of endpoints as a measure of health outcome. The EuroQol EQ-5D-3L will provide data for use in economic models and analyses including developing health utilities or quality-adjusted life years (QALYs).

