5.2.3 Timing of Dose Administration

Study treatments should begin on the day of randomization or within 3 days of randomization in both treatment arms. Study treatments and relevant safety assessments are cycle based. The day that the first dose of study treatment is received by each subject denotes Cycle 1 Day 1 (C1D1).

For the combination arm, each treatment cycle is 21 days, which is based on a Q3W dosing schedule of pembrolizumab. C1D1 of the combination arm should start when the subject can receive the first dose of pembrolizumab. The first dose of axitinib should start on the same day when first dose of pembrolizumab is administered, if possible, or start on the following day. For the sunitinib arm, each treatment cycle is 42 days. Study treatment will continue in 21-day or 42-day cycles, for the combination arm and sunitinib arm, respectively, until study treatments are permanently discontinued for the subject. The clinical visits and assessments are detailed in Section 6 – Trial Flow Chart.

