
diagnostic quality and within the 28 day window. See Sections 7.1.2.7.1 and 7.1.2.7.2 for additional imaging requirement at baseline and follow up if RCC metastatic lesions identified outside of the standard imaging assessment anatomic regions per protocol.
 
o. Imaging after randomization will be performed at Week 12 (84 days ±7 days), then Q6W (42 days ±7 days) through Week 54, then Q12W (84 days ±7 days) thereafter until PD is BICR verified. Imaging visit window may be ± 14 days after Week 104. Unscheduled imaging can be performed as clinically indicated. The timing of imaging assessments should follow calendar days from randomization and should not be adjusted for dose delays or cycle starts. Imaging anatomic coverage should be the same as that at screening; see Section 7.1.2.7.2 for details.
 
p. Subjects who discontinue treatment for reasons other than BICR verified PD should continue with imaging assessments per the protocol defined schedule as outlined in footnote “n” until: 1) PD is BICR verified, 2) initiation of a new anti-cancer treatment, 3) death, 4) withdrawal of consent or 5) study conclusion or early termination, whichever occurs first.
 
q. Baseline bone scan is required for all subjects. If a subject has a positive baseline bone scan, after randomization, bone scans will be performed at Week 18 (Day 126 ± 7 days) and should continue to be performed Q12W (84 days ±7 days) through Week 54, subsequently Q24W (168 days ±7 days) until PD is BICR verified or further confirmed by the investigator. The timing of imaging assessments should follow calendar days from randomization and should not be adjusted for dose delays or cycle starts. Bone scans must be performed for the confirmation of Complete Response (CR) for subjects with a positive bone scan at baseline.
 
r. A brain scan will be performed during screening for subjects with brain metastasis to ensure subject is stable. After randomization, brain imaging should be performed as clinically indicated and to confirm a CR in subjects with brain metastasis at baseline.
 
s. At each clinic visit, Quality of Life (QoL) measurements should be performed before all other study procedures and assessments, including the dosing of study medication. QoL will be assessed on D1 visit of every cycle from C1-C8, D1 visit of every other cycle from C9 to C19, D1 visit of every 4 cycles from C19 (approximately Week 54) until study treatment is discontinued. In addition, QoL is to be assessed at the Treatment Discontinuation visit and 30-day Safety follow-up visit. QoL is only assessed once if these two visits are combined.
 
t. Pregnancy tests – Urine or serum β-hCG: See Section 5.1.2 for pregnancy tests requirements for screening. If the randomization pregnancy test is more than 72 hours prior to the first dose of study treatment, it should be repeated. If urine pregnancy results are positive or cannot be confirmed as negative, a serum pregnancy test performed by the local study site laboratory will be required. Pregnancy tests (serum and/or urine tests) should be repeated if required by local guidelines. Monthly pregnancy testing should be conducted as per local regulations where applicable.
 
u. PT/INR, hematology, chemistry, urinalysis, and thyroid function testing will be performed at Screening (within 10 days of randomization), on Day 1 visit of every cycle (starting from C2), End of Treatment visit and at the Safety Follow-up visit. Routine safety laboratory values of chemistry and hematology results should be available prior to each pembrolizumab dosing.
 
v. Pre-dose trough PK and ADA samples for the pembrolizumab plus axitinib arm will be collected on Day 1 of Cycles 1, 3, 5, every 4 cycles thereafter (C9D1, C13D1, C17D1, ...) and 30 days after discontinuation. Pre-dose trough samples should be drawn within 24 hours prior to pembrolizumab infusion.
 
w. Additional post-dose peak PK samples will be drawn within 30 minutes after end of pembrolizumab infusion at Cycles 1 and 9. See Section 7.1.3.3 for additional guidance for PK sampling when dosing is interrupted/delayed.
 
x. Tumor tissue from an archival tissue sample or newly obtained biopsy should be submitted at Screening for biomarker analysis.
																	

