6.2 Trial Flow Chart (Sunitinib)

Trial Period:	Screening	Treatment Cycles (1 cycle = 42 days) ^a											End of Treatment	Post-Treatment			
		Cycles 1-4										To be repeated Beyond Cycle 6					
Treatment Cycle:	Screening	C1			C2			C3		C4		C5	C6	Discon	Safety Follow-up	Imaging Follow-up	Survival Follow-up
Scheduled clinic visit:		D1 ^a	D15	D29	D1	D29	D1	D29	D1	D29	D1	D1					
Clinic visit Windows (Days):	-28 to -1		± 3	± 3	± 3	± 3	± 3	± 3	± 3	± 3	± 3	± 3	End of Treatment	30 days from last dose (± 3 days)	Q6W or Q12W ^b (± 7 days)	Q12W ^c (± 7 days)	
ADMINISTRATIVE PROCEDURES																	
Informed Consent ^d	X																
Informed Consent - FBR (optional)	X																
Inclusion/Exclusion Criteria	X																
Subject Identification Card ^e	X												X				
Demographics & Medical History	X																
Prior and Concomitant Treatment/Medication Review ^f	X	X	X	X	X	X	X	X	X	X	X	X	X	X			
Post-study Anti-cancer Therapy Status														X	X	X	
Survival Status ^g		←-----														X	
STUDY DRUG ADMINISTRATION/ COMPLIANCE																	
Sunitinib Dosing ^h		X [scheduled dosing is 4 weeks on (D1-D28) and 2 weeks off (D29-D42) for each cycle] from C1D1															
Dispense Sunitinib and Dosing Diary ⁱ		X			X		X		X		X	X					
Review Sunitinib Compliance ⁱ					X		X		X		X	X	X				

Trial Period:	Screening	Treatment Cycles (1 cycle = 42 days) ^a											End of Treatment	Post-Treatment				
Treatment Cycle:	Screening	Cycles 1-4										To be repeated Beyond Cycle 6		Discon	Safety Follow-up	Imaging Follow-up	Survival Follow-up	
		C1			C2			C3		C4		C5	C6					
Scheduled clinic visit:		D1 ^a	D15	D29	D1	D29	D1	D29	D1	D29	D1	D1			End of Treatment	30 days from last dose (± 3 days)	Q6W or Q12W ^b (± 7 days)	Q12W ^c (± 7 days)
Clinic visit Windows (Days):	-28 to -1		± 3	± 3	± 3	± 3	± 3	± 3	± 3	± 3	± 3	± 3	± 3					
CLINICAL PROCEDURES/ ASSESSMENTS																		
AE Monitoring	X	X	X	X	X	X	X	X	X	X	X	X	X	X	X	X ⁱ	X ⁱ	
Full Physical Examination	X													X				
Directed Physical Examination			X	X	X	X	X	X	X	X	X	X	X					
Vital Signs ^k	X		X	X	X	X	X	X	X	X	X	X	X	X	X	X		
12-Lead ECG ^l	X						X					X			X			
KPS ^m	X			X	X	X	X	X	X			X	X		X			
EFFICACY MEASUREMENTS – TUMOR IMAGING																		
Chest, Abdomen, Pelvis	X ⁿ																X ^p	
Bone Scan	X ^{n,q}																X ^q	
Brain Scan	X ^{n,r}																X ^r	
PATIENT REPORTED OUTCOMES																		
QoL (FKSI-DRS, EORTC QLQ-C30, EQ-5D-3L) ^s		X		X	X	X	X	X	X	X	X	X	X	X	X	X		

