
s. At each clinic visit, Quality of Life (QoL) measurements should be performed before all other study procedures and assessments, including the dosing of study medication. QoL will be assessed D1 and D29 visits of C1-C4; D1 visit of C5 to C10, and D1 visit of every other cycle from C10 (D1C10, D1C12) (approximately Week 54) until study treatment is discontinued. In addition, QoL is to be assessed at the Treatment Discontinuation visit and 30-day Safety Follow-up visit. QoL is only assessed once if these two visits are combined.
 
t. Pregnancy tests – Urine or Serum β-hCG: See Section 5.1.2 for pregnancy tests requirements for screening. If the randomization pregnancy test is more than 72 hours prior to the first dose of trial treatment, it should be repeated. If urine pregnancy results are positive or cannot be confirmed as negative, a serum pregnancy test performed by the local study site laboratory will be required. Pregnancy tests (serum and/or urine tests) should be repeated if required by local guidelines. Monthly pregnancy testing should be conducted as per local regulations where applicable.
 
u. PT/INR, hematology, chemistry, urinalysis and thyroid function testing will be performed at Screening (within 10 days of randomization), C1D29, C2D1, C2D29, C3D1, C3D29, Day 1 of every cycle thereafter (C4D1, C5D1, C6D1,...), the End of Treatment visit and the Safety Follow-up visit.
 
v. Tumor tissue from an archival tissue sample or newly obtained biopsy should be submitted at screening for biomarker analysis.
 
w. Samples should be collected for planned analysis of the association between genetic variants in germline/tumor DNA and drug response. If a documented law or regulation prohibits (or if the IRB/IEC does not approve) sample collection for these purposes, then such samples should not be collected at the corresponding sites. Leftover DNA extracted from planned genetic samples will be stored for Future Biomedical Research only if the subject signs the FBR consent. If the planned genetic analysis is not approved, but FBR is approved and consent is given, this sample will be collected for the purpose of FBR.
 
x. Blood for ctDNA, TCR repertoire, RNA analyses and blood for serum/plasma biomarker analyses should be collected pre-dose according to time points on the flow chart. Leftover samples may be kept for Future Biomedical Research if the subject signs the FBR consent.
																		

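### Every post-baseline PRO week shared by the arms, including Week 42, falls at the end of sunitinib's scheduled break; label it so and add a phase-balanced contrast to Week 24

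*Combined protocol and SAP*

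**What the plan says.** PRO visits are set by footnote s of each flow chart.

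- Combination arm (Section 6.1): "QoL will be assessed on D1 visit of every cycle from C1-C8, D1 visit of every other cycle from C9 to C19", then "D1 visit of every 4 cycles from C19 (approximately Week 54) until study treatment is discontinued".
- Sunitinib arm (Section 6.2): "QoL will be assessed D1 and D29 visits of C1-C4; D1 visit of C5 to C10", then "D1 visit of every other cycle from C10 (D1C10, D1C12) (approximately Week 54").

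On cycle length, Section 5.2.3 says: "For the combination arm, each treatment cycle is 21 days". It gives 42 days for sunitinib. The sunitinib dosing row of Section 6.2 reads "scheduled dosing is 4 weeks on (D1-D28) and 2 weeks off (D29-D42) for each cycle". Section 5.2.3.2 has axitinib taken without planned breaks. Both footnotes have the questionnaires completed before dosing at a visit. Section 7.1.2.8 allows a window of 7 days either way and keeps PRO dates fixed when dosing is delayed.

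The QLQ-C30 secondary objective (Section 3.2) is "To assess the longitudinal score changes from baseline to 42 weeks". Section 4.2.3.3 repeats the 42-week time point, cites 10 points as the usual meaningful change, and promises p-values for treatment comparisons without a formal hypothesis or multiplicity adjustment. It lists three definitions of FKSI-DRS deterioration, with a 2-point threshold. One is unconfirmed. One must be "confirmed by the second adjacent 2 or more decrease from baseline". The third has the same form, measured from the nadir. Section 8.0 defers the PRO analysis plan to the sSAP, which is not among the documents reviewed.

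**The concern.** A PRO score on an intermittent regimen depends on where in the cycle it is taken. If the arms are compared at weeks when one has just finished a drug-free interval and the other is on continuous treatment, the contrast mixes the treatment effect with a phase effect. Section 4.2.3.3 itself says that these scores reflect tolerability as well as disease.

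The QLQ-C30 global scale and the FKSI-DRS are the trial's key PRO endpoints. A Week 42 difference, with its p-value, could be read as a comparison of the two regimens as patients live through them. If sunitinib is sampled only after a break, that reading may be off by a meaningful part of the 10-point threshold. No text in the documents mentions cycle phase in a PRO comparison.

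**Working it through.** **Step 1: reproduce the plan's own calendar.** Combination week = (cycle − 1) × 3. Sunitinib week = (cycle − 1) × 6 + (day − 1)/7. Combination C19D1 = 18 × 3 = 54 and sunitinib C10D1 = 9 × 6 = 54. Both match the approximate Week 54 in the two footnotes.

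**Step 2: list the visits to Week 42.**

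| Arm | PRO weeks |
|---|---|
| Combination, D1 | 0, 3, 6, 9, 12, 15, 18, 21, 24, 30, 36, 42 |
| Sunitinib, D1 | 0, 6, 12, 18, 24, 30, 36, 42 |
| Sunitinib, D29 | 4, 10, 16, 22 |

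**Step 3: intersect.** Week 0 is shared and is pre-treatment. The shared post-baseline weeks to Week 42 are 6, 12, 18, 24, 30, 36 and 42. All seven are sunitinib D1 visits, 14 days after the last scheduled dose. Carried on through combination C35, the shared weeks add 48, 54, 66, 78, 90 and 102, making 13, again all D1. Week 42 is sunitinib C8D1 (off drug Weeks 40 to 42) and combination C15D1. A visit 7 days early would still be inside the break. The Section 6.1 chart row also appears to mark combination C10 and C12 (Weeks 27 and 33). Sunitinib has no PRO at Week 28 or 34, so nothing changes.

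**Step 4: what the D29 visits offer.** Four can be paired with a combination visit one week earlier: Weeks 4/3, 10/9, 16/15 and 22/21. There are no D29 visits after Week 22. D29 makes up 4 of 8 post-baseline sunitinib visits to Week 24, and 4 of 11 to Week 42.

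**Step 5: size, under an assumption.** Let d be the drop in score at the end of dosing relative to the end of the break. The documents give no value.

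- *Step pattern* (full deficit on all 28 dosing days, none on the 14 off days): mean deficit = d × 28/42 = 2d/3. D1 overstates the cycle average by 2d/3; D29 understates it by d/3.
- *Linear pattern* (steady fall over 28 days, steady recovery over 14): mean deficit = d/2. D1 overstates by d/2; D29 understates by d/2.

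| d (points) | D1 overstates by | D29 understates by |
|---|---|---|
| 2.5 | 1.3–1.7 | 0.8–1.3 |
| 5 | 2.5–3.3 | 1.7–2.5 |
| 10 | 5.0–6.7 | 3.3–5.0 |

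D29 alone is therefore no neutral substitute; it leans against sunitinib. The cycle average weights D29 to D1 as 28:14 under the step pattern and equally under the linear one. A trapezoidal area under the curve to Week 24 gives equal weighting: D29 visits carry 4 × 3 = 12 weeks, and D1 visits carry 2 + 3 × 3 + 1 = 12.

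**Step 6: deterioration.** From C1D29 to C5D1 the sunitinib sequence alternates D29, D1, D29, D1, so one of any two adjacent visits is an end-of-break visit. In the combination arm both adjacent visits fall under scheduled axitinib. If scores recover off drug, both confirmed definitions are harder to meet on sunitinib in C1–C4. The unconfirmed definition counts any single D29 drop and can lean the other way. After Week 22 only D1 visits remain.

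**The case against.** The strongest reply is that the documents do not specify the analysis being criticised. PRO methods are left to the sSAP, nothing restricts comparisons to coincident weeks, and the 42-week QLQ-C30 results are to be described, with p-values but no formal hypothesis. The schedule also collects four D29 assessments per sunitinib subject. This stands to the extent that the sSAP may already deal with phase. It does not remove the point, because 42 weeks is the named time point and the sunitinib score there is nominally an end-of-break score.

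A second reply is that the break is part of the regimen. That is true, but a comparison of whole regimens needs scores that represent the whole cycle, and sunitinib is dosed on 28 of 42 days.

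A third reply is that direction is unproven. This stands in part. Table 11 withholds sunitinib until toxicity recovers, and Section 4.2.3.3 ties the scores to tolerability, so easing off drug is plausible. But no on-off difference and no PRO recall period are given. Phase is also only nominal: Section 5.2.3.4 lets a sunitinib cycle restart after a long interruption, while PRO dates stay fixed.

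A reader might infer that the trial cannot answer its PRO question fairly, or that the Week 42 comparison is known to favour sunitinib. The documents support neither. The D29 visits allow a phase-balanced contrast to Week 24, and the favourable direction is an inference. Nor do all PRO endpoints tilt one way, since unconfirmed deterioration can tilt against sunitinib.

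**Conclusion.** The schedule imbalance is a matter of calendar arithmetic and holds without assumptions about symptoms. All 13 shared post-baseline weeks through combination C35, Week 42 among them, come at the end of sunitinib's scheduled break, and the last sunitinib D29 PRO is at Week 22.

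The size is conditional. If on-drug scores are d points worse, Week 42 overstates sunitinib's cycle-average score by about d/2 to 2d/3: a quarter to a third of the 10-point threshold for d = 5, and half to two-thirds of it for d = 10. This rests on an assumed d, on the two simple within-cycle patterns, and on subjects keeping to the nominal cycle.

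Two of the three FKSI-DRS deterioration definitions are also affected in sunitinib cycles 1 to 4. The Week 42 contrast cannot be corrected from collected visits, only labelled and probed. This is an inexpensive improvement to the analysis, and it leaves the primary endpoints untouched.

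**What to change.** In the sSAP, before any PRO analysis:

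1. Keep the Week 42 analysis and label it an end-of-break comparison for sunitinib.
2. Alongside it, pre-specify a between-arm time-averaged change from baseline to Week 24 for QLQ-C30 global health status and FKSI-DRS (area under the curve or phase-weighted). Use all collected D1 and D29 sunitinib visits and all combination visits. Take cycle phase from actual dosing dates, and show results under both 28:14 and equal weighting.
3. Report the within-subject D29-to-D1 difference by cycle for sunitinib C1–C4. Use one-half to two-thirds of it only as a sensitivity shift at Week 42, stating the assumption that the early-cycle difference persists. Shifting by the whole difference would estimate the end-of-dosing score and overcorrect.
4. Report confirmed and unconfirmed deterioration side by side with the limitation stated. Do not make an arm-specific confirmation rule the main definition. Confirming one D29 drop at the next D29, for example, is undefined at C4D29 and sets a 6-week interval against 3 weeks in the combination arm.

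The cost is some sSAP text and a little more modelling. Randomisation is complete (861 subjects, Section 8.9), no visits are added, and no alpha is involved. The drawback is that the phase-balanced contrast covers 24 weeks, not 42. If the sSAP already handles cycle phase, the sponsor need only confirm it.

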6.3 Trial Flow Chart Second Course Phase (Retreatment)

Second course re-treatment subjects may receive up to 17 cycles (approximately 1 year) of pembrolizumab therapy.

Trial Period:	Treatment Cycles												End of Treatment	Post-Treatment		
	Cycles 1-8								To be repeated Beyond 12 Cycles							
Treatment Cycle/Title:	1	2	3	4	5	6	7	8	9	10	11	12	Discon	Safety Follow-up	Imaging Follow-up Visits	Survival Follow-up
Scheduling Window (Days):	± 3	± 3	± 3	± 3	± 3	± 3	± 3	± 3	± 3	± 3	± 3	± 3	At time of Discon	30 days from last dose (± 3 days)	Every 6 or 12 weeks post discon (± 7 days)	Every 12 weeks (± 7 days)
ADMINISTRATIVE PROCEDURES																
Re-treatment Criteria	X															
Concomitant Medication Review	X	X	X	X	X	X	X	X	X	X	X	X	X	X		
Pembrolizumab Administration	X ^a	X	X	X	X	X	X	X	X	X	X	X				
Post-study Anti-cancer Therapy Status															X	X
Survival Status ^b	←-----Dashed Line-----→														X	
CLINICAL PROCEDURES/ASSESSMENTS																
AE Monitoring	X	X	X	X	X	X	X	X	X	X	X	X	X	X ^c	X ^c	
Full Physical Examination													X			
Directed Physical Examination	X	X	X	X	X	X	X	X	X	X	X	X				
Vital Signs ^d	X	X	X	X	X	X	X	X	X	X	X	X	X			
Karnofsky Performance Status ^e	X	X	X	X	X	X	X	X	X	X	X	X	X			
EFFICACY MEASUREMENTS																
Tumor Imaging - chest, abdomen, pelvis (CAP)									X ^f						X ^g	
Tumor Imaging – bone scan									X ^{f,h}						X ^h	
Tumor Imaging – brain scan									X ⁱ						X ⁱ	
LABORATORY PROCEDURES/ASSESSMENTS: ANALYSIS PERFORMED BY LOCAL LABORATORY																
Pregnancy Test – Urine or Serum β-hCG ^j	X															
PT/INR	X ^k															
Hematology ^l	X ^k	X	X	X	X	X	X	X	X	X	X	X	X	X		

Trial Period:	Treatment Cycles												End of Treatment	Post-Treatment		
	Cycles 1-8								To be repeated Beyond 12 Cycles					Discon	Safety Follow-up	Imaging Follow-up Visits
Treatment Cycle/Title:	1	2	3	4	5	6	7	8	9	10	11	12	At time of Discon			
Scheduling Window (Days):	± 3	± 3	± 3	± 3	± 3	± 3	± 3	± 3	± 3	± 3	± 3	± 3	At time of Discon	30 days from last dose (± 3 days)	Every 6 or 12 weeks post discon (± 7 days)	Every 12 weeks (± 7 days)
Chemistry ^l	X ^k	X	X	X	X	X	X	X	X	X	X	X	X	X		
Urinalysis ^m	X ^k	X		X		X		X		X		X	X	X		
T3, FT4, and TSH ^m	X ^k	X		X		X		X		X		X	X	X		

- a. Cycle 1 re-treatment must be given within 3 days.
- b. Following documented disease progression, or the start of new anticancer treatment; contacts are approximately every 12 weeks by telephone. Updated survival status may be requested by the Sponsor at any time during the course of the study. Upon Sponsor notification, all participants who do not/will not have a scheduled study visit or study contact during the Sponsor defined time period will be contacted for their survival status (excluding participants that have a death event previously recorded).
- c. After the end of treatment each subject will be followed for 30 days for AE monitoring (SAEs will be collected for 90 days after the end of treatment or 30 days after the end of treatment if the subject initiates new anti-cancer therapy, whichever is earlier). See Section 7.2.3.1 for details.
- d. Height will be measured prior to re-treatment. Vital signs will be performed within 10 days prior to the first re-treatment dose of pembrolizumab.
- e. Karnofsky Performance Status will be performed prior to re-treatment (within 10 days prior to the first re-treatment dose of pembrolizumab) and Day 1 visit of every cycle.
- f. The initial tumor imaging will be performed within 28 days prior to first re-treatment cycle and then every 12 weeks thereafter (84 days ±7 days).
- g. Subjects who discontinue treatment for reasons other than BICR verified PD should continue with imaging assessments per the protocol defined schedule until 1) PD is BICR verified or further confirmed by the investigator, 2) initiation of a new anti-cancer treatment, 3) death or 4) withdraw of consent from trial or 5) study conclusion or early termination, whichever occurs first.
- h. A bone scan will be performed prior to first re-treatment cycle. If a subject has a positive bone scan, bone scans will be performed additionally every 24 weeks thereafter (168 days ±14 days). The timing of imaging assessments should follow calendar days from C1 of re-treatment and should not be adjusted for dose delays or cycle starts. Bone scans must be performed for the confirmation of Complete Response (CR).
- i. A brain scan is as clinically indicated but is required for subjects with brain metastasis if the subject achieves a CR.
- j. For women of childbearing potential, a urine pregnancy test should be performed within 72 hours prior to first dose of trial re-treatment. If urine pregnancy results are positive or cannot be confirmed as negative, a serum pregnancy test performed by the local study site laboratory will be required. Pregnancy tests (serum and/or urine tests) should be repeated if required by local guidelines. Monthly pregnancy testing should be conducted as per local regulations where applicable.
- k. Laboratory tests for determining eligibility are to be performed within 10 days prior to the first re-treatment dose of pembrolizumab.
- l. Hematology and chemistry assessments will be performed prior to re-treatment, Day 1 visit of every cycle, at treatment discontinuation, and 30 days after discontinuation.
- m. Urinalysis and T3, FT4, and TSH will be performed prior to re-treatment, then every other cycle starting at Cycle 2, at treatment discontinuation, and 30 days after discontinuation.

